			C1 D8	C1 D28	C2 D28	C4 D28	C6 D28	C8 D28	C10 D28	C12 D28	C16 D28	C20 D28	C24 D28 w	C30 b D28 onwards			
Study Day	Day – 28 to Day – 1	Day 1	Day 8	Day 28	Day 56	Day 112	Day 168	Day 224	Day 280	Day 336	Day 448	Day 560	Day 672				
Window (days)			Day 4-14	± 3	± 3	± 7	± 7	± 7	± 7	± 7	± 7	± 7	± 7	± 7	+ 7	+ 7	
PK blood samples u			X														8.5.1
AEs v	X	X	←	=====	=====	=====	=====	=====	=====	=====	=====	=====	=====	→			8.3
Concomitant medication/ procedures	X	X	←	=====	=====	=====	=====	=====	=====	=====	=====	=====	=====	=====	→		6.5

a The 28-day screening period will commence on the date the ‘Screening Visit’ transaction is registered in IRT system. Visit schedule should always be calculated in relation to C1D1. Visits should not be skipped or overwritten in IRT. If a visit (+ visit window) is missed, the visit should be completed as the earliest opportunity. If there is a long gap between the scheduled and actual visit, please check with global study team how visits are to be recorded.

b From Cycle 30 onwards, for all participants remaining on study intervention, assessments will be performed every 6 cycles with the exception of ophthalmic assessments (see footnote l) and pregnancy assessments (see footnote m).

c The EoT visit will be performed for participants who permanently discontinue study intervention for any reason (except for death, lost to follow-up or withdrawal of consent). The EoT visit should be performed as soon as possible after the decision to discontinue treatment permanently has been made. If EoT is >30 days after last treatment dose, then the EoT assessments can also function as the 30-Day Safety follow-up visit.

d Screening tests should be performed within 28 days before the first administration of study intervention, unless otherwise indicated. Written informed consent and any locally required privacy act document authorisation must be obtained prior to performing any protocol-specific procedures, including screening/baseline evaluations.

e Every effort should be made to minimise the time between randomisation and starting treatment (maximum interval of 3 business days of randomisation).

f Assessment of baseline disease characteristics includes documenting location of the target and non-target PN (if applicable) and any PN-related symptoms and results of any previous genetic testing for NF1.

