If selumetinib is approved locally and reimbursed for use in adult patients with NF1 who have symptomatic, inoperable PN, participants should be switched to the commercial supply at the end of the study. However, if the participant is unable to access the commercial supply and they are still receiving clinical benefit, AstraZeneca and the Investigator will discuss how the participant could continue to receive selumetinib if he/she is benefiting from treatment.

After study intervention discontinuation, all participants will undergo an end-of-treatment visit and will be followed up for safety assessments 30 (+ 7) days after their last dose of study intervention (ie, the safety follow-up visit), unless EoT is performed more than 30 days after last treatment dose, then the EoT assessments can also function as the 30-Day Safety follow-up visit.

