#### **8.2.5      Echocardiogram/Cardiac MRI**

An ECHO or cardiac MRI scan to assess LVEF will be performed at the visits as shown in SoA. The modality of the cardiac function assessments must be consistent for a given participant (ie, if ECHO is used for the screening assessment for a given participant, then ECHO should also be used for subsequent scans for that participant). The participants should also be examined using the same machine and operator whenever possible, and quantitative measurements should be taken (ie, accurate to 1% and not estimated to 5%).

Left ventricular ejection fraction, end diastolic and end systolic left ventricular volumes should be recorded at each ECHO or cardiac MRI assessment.

Participants experiencing an asymptomatic LVEF reduction or left ventricular systolic dysfunction should be managed according to the algorithm provided in Appendix [H 1](#).

Participants who have a drop in LVEF of  $\geq 10$  percentage points from baseline and to below the LLN at the time of selumetinib discontinuation should, where possible, have a follow-up ECHO or cardiac MRI, ECG, vital signs, and weight performed after 30 days to evaluate the potential for reversibility.

An ECHO or cardiac MRI will also be carried out if a participant develops signs and/or symptoms suggestive of deterioration in left ventricular function/cardiac event.

A further ECHO or cardiac MRI should be performed as part of the assessment package for any cardiorespiratory AE with no obvious diagnosis (obvious causes will be managed in accordance with local clinical practice) and additionally at the discretion of the investigator if clinically indicated.

If a participant has had an ECHO/cardiac MRI scan performed within 4 weeks prior to study intervention discontinuation, the discontinuation visit ECHO/cardiac MRI scan is not required unless clinically indicated.

Situations in which ECHO/cardiac MRI scan results should be reported as AEs are described in Section 8.3.5.

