The interim analysis (data cut-off [DCO]1) will occur after the 100th randomised patient has had the opportunity to complete their end of Cycle 16 assessment, and the primary analysis (DCO2) will occur after the last patient dosed (LPD; the last patient receiving first dose) has had the opportunity to complete their end of Cycle 16 assessment. If the interim analysis DCO (DCO1) is due to take place within approximately 4 months of the primary analysis DCO (DCO2), then the interim analysis may not be performed and only the primary analysis will be performed. The primary analysis of the ORR will take place at the end of the Cycle 16 landmark and will be assessed in all randomised patients with measurable target PN at baseline per ICR. The 1st key secondary endpoint of change from baseline in PAINS-pNF chronic target PN pain intensity at Cycle 12 will be assessed in patients with a PAINS-pNF chronic target PN pain intensity score of \geq 3 at baseline and at least one post baseline average cycle PAINS-pNF chronic target PN pain intensity score. The 2nd key secondary endpoint of change from baseline in Plexiform Neurofibroma Quality of Life scale (PlexiQoL) total score at Cycle 12 will be assessed in full analysis set (FAS) patients with a baseline PlexiQoL total score and at least one post-baseline PlexiQoL

total score. The analysis of the primary endpoint and of the two key secondary endpoints will be comparative between selumetinib and placebo by the end of the randomised period.

The final analysis (final DCO) will occur approximately 24 cycles post LPD. The proposed duration for the study is approximately 24 months from the LPD to provide efficacy data as well as further safety and tolerability data. Following the end of the study, a mechanism will be in place to ensure that patients will be able to continue taking selumetinib as long as they derive clinical benefit, as judged by the investigator and in the absence of discontinuation criteria. After study intervention discontinuation, all patients will undergo an end-of-treatment visit and will be followed up for safety assessments 30 (+ 7) days after their last dose of study intervention (i.e., the safety follow-up visit).

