3.3.2.3 On-Treatment Safety Period

For the purposes of summarising safety data assessed at visits, in addition to baseline data, only on-treatment data are included in the summary tables. On-treatment data will be defined as data from the first dose of study intervention until the last dose of study intervention + 30 days.

The On-Treatment Safety Period will be further subset into the On-treatment Safety Randomised Period and On-selumetinib Safety Period.

If the On-Treatment Safety Period of a patient is still ongoing at the time of the analysis, their on-treatment safety period will be truncated at the DCO date, and any measurement/event with a start date after the DCO date will be presented at a later DCO.

On-treatment Safety Randomised Period.

The on-treatment safety randomised period for patients receiving selumetinib in the randomised period will be defined as the date from the first dose of study intervention until the first date when the selumetinib kit(s) are dispensed as recorded in the drug accountability form at or after the Cycle 12 Day 28 visit date or 30 days after study intervention discontinuation or up to one day prior to start of subsequent therapy, whichever occurs first.

The on-treatment safety randomised period for patients receiving only placebo in the randomised period will be defined as the date from the first dose of study intervention until the date when the first selumetinib kit(s) are dispensed as recorded in the drug accountability form (crossover date) or 30 days after placebo discontinuation or up to one day prior to the start of subsequent therapy, whichever occurs first.

If the on-treatment randomised period of a patient is still ongoing at the time of the analysis, their on-treatment randomised period will be truncated at the DCO date, and any measurement/event with a start date after the DCO date will be presented at a later DCO.

On-Selumetinib Safety Period

The on-selumetinib safety period will be defined as the date from the first dose of selumetinib until 30 days after the last dose of selumetinib or up to one day prior to the start of subsequent therapy, whichever occurs first.

The baseline definition for patients receiving placebo in the randomised period and then crossing over to selumetinib either on Cycle 13 Day 1 or earlier in the case of progression will differ for the on-treatment safety randomised period and the on-selumetinib period as described in Section [3.3.1](#).

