3.3.3 Visit Window

Time windows will be defined for any presentations that summarise values by visit. The following conventions will apply:

- Study day references the date of first dose of study intervention as Day 1.
- The time windows will be exhaustive so that data recorded at any timepoint have the potential to be summarised. Inclusion within the time window will be based on the actual date and not the intended date of the visit.
- The window for visits following baseline is constructed in such a way that the upper limit of the interval falls halfway between the two visits (the lower limit of the first post-baseline visit is Day 2). If an even number of days exists between two consecutive visits, then the upper limit is taken as the midpoint value minus 1 day.
- For summaries showing the maximum or minimum values, the maximum/minimum value recorded on treatment during the randomised period

and the on-selumetinib period (as defined in Section 3.3.2.3) will be used (regardless of where it falls in an interval).

- Listings display all values contributing to a timepoint for a patient.
- For visit-based summaries/analyses, if there is more than one value per patient within a time window, then the closest value to the scheduled visit date will be summarised or the earlier, in the event the values are equidistant from the nominal visit date. The listings will highlight the value for the patient that contributed to the summary table, wherever feasible.

Note: In summaries of extreme values, all post-baseline values collected are used, including those collected at unscheduled visits regardless of whether the value is closest to the scheduled visit date.

Note: For the purpose of the visit-based summaries of efficacy data (except tumour volumes and response), the EOT visit will be mapped into one of the planned visit windows. For visit-based safety summaries and for tumour volume and response summaries, the EOT and/or Safety Follow-up Visit will be summarised apart.

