4.6.3 Clinical Laboratory, Blood Sample

4.6.3.1 Definitions and Derivations

Blood samples for the determination of clinical chemistry and haematology will be taken at the visits indicated in the CSP.

The rules described in Sections [3.3.1](#), [3.3.3](#), [3.3.4](#), and [3.3.5](#) of this document considering definition of baseline, visit windows, and handling multiple records and records above or below the limit of quantification are followed.

Absolute values are compared to the reference range and classified as low (below range), normal (within range or limits of range), and high (above range). Local reference ranges are used for the primary interpretation of laboratory data.

Changes from baseline in clinical chemistry and haematology will be calculated for each post-dose visit on treatment, where on treatment includes all data collected between the first dose of selumetinib until the earlier of last dose of study intervention + 30 days, or DCO.

All laboratory results will be converted to standard units, and CTCAE grades (version 5.0) will be derived at each visit according to the CTCAE grade criteria. Parameters for which CTCAE grades are defined may have both high and low range values, CTCAE grades will be calculated for each set of high and low values in those cases. Laboratory parameters that will be summarised, along with details of whether maximum and/or minimum are of interest and availability of CTCAE grading, are given in [Table 17](#).

Table 17: Haematology and Clinical Chemistry Parameters – Minimum/Maximum of Interest

Laboratory assessment	Maximum of interest	Minimum of interest	CTCAE grading available
ALT	Yes		Yes
AST	Yes		Yes
Alkaline phosphatase	Yes		Yes
Total bilirubin	Yes		Yes
Magnesium	Yes	Yes	Yes
Sodium	Yes	Yes	Yes
Potassium	Yes	Yes	Yes
Creatinine	Yes		Yes
Total calcium	Yes	Yes	No
Blood urea nitrogen	Yes		No
Creatine kinase	Yes		Yes
Haemoglobin	Yes	Yes	Yes
Lymphocytes (absolute)	Yes	Yes	Yes

Table 17: Haematology and Clinical Chemistry Parameters – Minimum/Maximum of Interest

Laboratory assessment	Maximum of interest	Minimum of interest	CTCAE grading available
Neutrophils (absolute)		Yes	Yes
Leukocytes (absolute)		Yes	Yes
Total red blood cell count		Yes	No
Platelets		Yes	Yes
Albumin		Yes	Yes
Total Protein		Yes	No
Amylase	Yes		Yes
Gamma-glutamyl transferase	Yes		Yes
Phosphate	Yes	Yes	No

ALT, alanine aminotransferase; AST, aspartate aminotransferase; CTCAE, Common Terminology Criteria for Adverse Events.

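### The SAP's 30-day cut-off for safety visit data admits only one of the eight permitted days for the Safety Follow-up visit, and so conflicts with its own plan to summarise that visit separately

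*SAP*

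**What the plan says.** SAP 3.3.2.3 governs safety data assessed at visits. Beyond baseline, "only on-treatment data are included in the summary tables", and the period is fixed as follows: "On-treatment data will be defined as data from the first dose of study intervention until the last dose of study intervention + 30 days". The section then defines sub-periods from which the tables are built: a safety randomised period for each arm, and an on-selumetinib period. Each carries its own 30-day limit. SAP 4.6.3.1 repeats the limit for laboratory changes: "until the earlier of last dose of study intervention + 30 days, or DCO". SAP 4.6.3.2 (laboratory), 4.6.6.2 (vital signs) and 4.6.8.2 (ECHO/cardiac MRI) each refer back to 3.3.2.3 for what may be tabulated.

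The visit itself is set later. In SAP 1.1 participants are to be "followed up for safety assessments 30 (+ 7) days after their last dose of study intervention", and Protocol 4.1 agrees: they "will be followed up for safety assessments 30 (+ 7) days after their last dose of study intervention". The Schedule of Activities gives this visit a window of +7 days with no early side. The schedule's footnote on EoT adds: "If EoT is >30 days after last treatment dose, then the EoT assessments can also function as the 30-Day Safety follow-up visit".

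SAP 3.3.3 says that in visit-based safety summaries "the EOT and/or Safety Follow-up Visit will be summarised apart".

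**The concern.** A follow-up visit held on days 31 to 37 complies with the protocol and still fails the filter for the tables. SAP 3.3.3 promises a separate summary of that visit. Read literally, 3.3.2.3 leaves that summary with day-30 visits only.

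Laboratory tests and vital signs are routine at this visit. For a participant with a marked LVEF fall at discontinuation, Protocol 8.2.5 asks for repeat ECHO or cardiac MRI, ECG, "vital signs, and weight performed after 30 days to evaluate the potential for reversibility". All these results come from people who have stopped drug. At stake is whether the planned tables can show recovery, or worsening that first appears after stopping.

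**Working it through.** No sample size, power or alpha figure is involved, and the plan states no figure to reproduce. The check is a count of whole days after last dose.

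**Inputs**
- Earliest scheduled follow-up visit: day 30. Latest: day 30 + 7 = day 37 (Protocol 4.1, Schedule of Activities, SAP 1.1).
- Last day admitted to the tables: day 30 (SAP 3.3.2.3, 4.6.3.1).

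**Overlap**
- Permitted days: 37 − 30 + 1 = 8.
- Permitted days at or before day 30: 1.
- Share of permitted days admitted: 1/8 = 12.5%.

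**Share of visits lost.** This is not the same quantity. For visits held inside the window, share excluded = 1 − share held on exactly day 30. The documents give no visit dates, so the day-30 share is an assumption:

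| Assumed share on exactly day 30 | Share excluded |
|---|---|
| 100% | 0% |
| 75% | 25% |
| 50% | 50% |
| 25% | 75% |
| 12.5% (even spread over the 8 days) | 87.5% |
| 0% | 100% |

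**EoT visit serving as follow-up.** Such a visit is by definition later than day 30 after last dose, so it fails any limit counted from last dose. But the two randomised-period definitions in SAP 3.3.2.3 count 30 days from discontinuation of study intervention (or of placebo). SAP 4.6.1.1 recognises that a participant may discontinue permanently during a dose interruption. If discontinuation falls g days after last dose, the randomised-period limit lies at day 30 + g after last dose, and a late EoT visit can fall inside it. The overall and on-selumetinib definitions count from last dose and would exclude it. The SAP does not say which prevails.

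**Extreme values.** One bullet in SAP 3.3.3 confines maxima and minima to values recorded on treatment under 3.3.2.3. The note that closes the same list, and SAP 3.3.4, use every post-baseline value. The shift tables in 4.6.3.2 and 4.6.8.2 are framed as worst or maximum grade on treatment. A day-31 to day-37 value is therefore in or out depending on which sentence is followed.

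**With the limit at last dose + 37 days:** 8 of 8 permitted days are admitted, subject to the other stopping rules.

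**The case against.** The strongest reply is that SAP 3.3.3 already rescues the visit, since it says the visit is summarised on its own and that the time windows are meant to be exhaustive. That may well be the intention. But the sentence settles where the visit is displayed, and it does not lift the data restriction in 3.3.2.3 that the laboratory, vital-sign and ECHO sections invoke by section number. At best the two sections conflict and a programmer must choose.

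The second reply is that 30 days is a coherent choice: it matches the treatment-emergent AE window, and the protocol describes selumetinib as having a short half-life. This stands as a reason to leave the AE window alone. It does not explain planning a follow-up summary that the cut-off nearly closes.

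Three further limits on the point stand in full:
- Nothing is deleted. Vital-sign, ECHO/cardiac MRI and protocol-specified laboratory data are listed.
- Follow-up ECHO is required only after abnormal findings at discontinuation or EoT (Schedule of Activities), so few LVEF results are involved.
- A recovered value cannot change a worst-grade table. Only new worsening after day 30 could. Clinically relevant deterioration would also be reported as an AE (Protocol 8.3.5), although an onset after day 30 would lie outside the treatment-emergent window.

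A reader might infer from the 1-in-8 overlap that nearly all follow-up results, or 87.5% of them, are lost. That needs visits spread evenly over the window, which the documents do not state. A reader might also infer that every late EoT visit is excluded. The randomised-period limits, counted from discontinuation, make that insecure.

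**Conclusion.** The point holds as an internal conflict in the SAP with a practical consequence. The cut-off for tabulated visit data and the scheduled follow-up window meet on one day of eight, while another section plans a separate summary of that visit. The one-day overlap is fixed by the text. The proportion of visits lost is not, and can be anything from 0% to 100%.

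The effect is confined to participants who stop study drug, and mainly to the separate follow-up summaries of laboratory, vital-sign and ECHO/LVEF data. Worst-grade tables are affected only by late new worsening, and there the SAP's own wording is inconsistent. No efficacy analysis or type I error is touched.

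This rests on two readings: that the window is counted in whole days with day 30 included, and that the reference to laboratory data in SAP 4.6.8.2 is a wording slip for ECHO data. The matter should be settled before programming because it concerns a planned safety summary and is cheap to resolve.

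**What to change.** Choose one of two changes in SAP 3.3.2.3:
1. State that the nominal Safety Follow-up visit, and an EoT visit serving as it, is included in the separate follow-up summary whatever its date.
2. Extend the limit for visit-based safety data to last dose + 37 days.

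In both cases keep the stops at crossover, start of subsequent therapy and DCO. The first is the safer choice, because it also covers a combined EoT/follow-up visit held after day 37.

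The edit must reach all five places where the 30-day limit appears: the overall definition, the two randomised-period definitions and the on-selumetinib definition in 3.3.2.3, and the laboratory sentence in 4.6.3.1. Changing the overall sentence alone would not help, since the tables are built by sub-period. At the same time, make SAP 3.3.3 and 3.3.4 agree on whether extreme values use on-treatment values or all post-baseline values, and use a single reference date (last dose or discontinuation) in 3.3.2.3. Leave the 30-day treatment-emergent AE window unchanged.

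The cost is a few sentences and the matching programming rule. The downside is small: under the second option, results up to 7 days further from last dose enter the tables (under the first, a late visit could be further out), and the visit-data window no longer matches the AE window. A footnote on the affected tables would cover that.

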3.3.2.4 Treatment-emergent Periods

The analysis of treatment-emergent adverse events (TEAEs) and concomitant medication will be performed separately for TEAEs occurring/concomitant medication taken during the safety randomised period and TEAEs occurring/concomitant medication taken during the on-selumetinib period. While the analysis of TEAEs in the safety randomised period will be comparative of the two treatment groups, TEAEs presented for the on-selumetinib period will be not comparative due to the different exposure periods. To note, the two safety analysis periods are not mutually exclusive.

TEAEs and Concomitant Medication during the Safety Randomised Period

For patients receiving any selumetinib in the safety randomised period, an adverse event (AE) or a concomitant medication is considered treatment emergent during the safety randomised period if the start date/time of the event or worsening date/time (only for AEs) occurs between the date of first dose of study intervention (Cycle 1 Day 1) and last dose of Cycle 12 or date of study intervention discontinuation (end of treatment [EOT]) + 30 days or DCO date, whichever comes first.

For patients receiving placebo in the safety randomised period, an AE or a concomitant medication is considered treatment emergent during the safety randomised period if the start date/time of the event, or worsening date/time of an AE occurs between the date of first dose of placebo (Cycle 1 Day 1) and the crossover date or date of early placebo discontinuation + 30 days or DCO, whichever comes first.

A worsening is defined as having any on-treatment severity during the safety randomised period worse than the baseline severity. The reported severity of an AE that is treatment emergent during the safety randomised period is given by the maximum Common

Terminology Criteria for Adverse Events (CTCAE) grade recorded any time on-treatment during the safety randomised period. The reported outcome of an AE will be the last outcome corresponding to the maximum CTCAE grade recorded on-treatment in the safety randomised period. Seriousness and causality during the randomised period will also be reported as the worst value recorded in the safety randomised period.

TEAEs and Concomitant Medication during the On-Selumetinib Period

An AE or a concomitant medication is considered treatment-emergent during the on-selumetinib period if the start date/time of the event, or worsening date/time of a AE occurs between the first dose of selumetinib (which will be Cycle 1 Day 1 for patients receiving selumetinib in the safety randomised period and the date of the crossover for patients receiving placebo in the safety randomised period) until 30 days after the last dose of selumetinib or up to DCO, whichever comes first.

A worsening is defined as having any on-treatment severity during the on-selumetinib period worse than the severity of the safety randomised period. Worsening in the on-selumetinib period will be assessed by comparing to the last-recorded value in the safety randomised period.

For AEs of placebo patients starting during the safety randomised period and worsening during the On-Selumetinib period, the stop date of the event during the safety randomised period will be one day prior to the date of the first worsening after crossing over, while the start date of the event during the on-selumetinib period will be equal to the date of first worsening after crossing over.

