4.1.8 Prior/Concomitant Medications and Procedures

4.1.8.1 Definitions and Derivations

Medications received prior to, concomitantly, or post study intervention discontinuation are coded using the latest World Health Organisation (WHO) Drug Dictionary.

For the purpose of inclusion in prior and/or concomitant medication or therapy summaries, incomplete medication start and stop dates are imputed as detailed in Section [3.3.5.1](#).

Prior, concomitant medications are defined based on imputed start and stop dates as follows:

- Prior medications are those taken prior to study intervention with a stop date prior to the first dose of study intervention.
- Concomitant medications are those with a stop date on or after the first dose date of study intervention (and could have started prior to or during treatment).

Missing coding terms are listed and summarised as “Not coded”.

Procedures will be coded using MedDRA (using the latest MedDRA version).

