4.1.8.2 Presentation

The following summaries will be produced by treatment group:

- Summary of prior medications
- Summary of allowed concomitant medications
- Summary of disallowed concomitant medications

The summary tables of allowed and disallowed concomitant medications will be presented for medications during the on-treatment safety randomised period using the FAS and the on-selumetinib safety period using the Extended Selumetinib FAS. Definitions of the safety randomised period and on-selumetinib safety period are given in Section [3.3.2.3](#).

All concomitant medications will be listed.

Procedures will not be summarised but only listed.

Medication and procedure data will be presented for all patients in the FAS.

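### SAP 3.3.2.4 assigns concomitant medication to a period by start date, which conflicts with its own stated aim and with 4.1.8; applied as written, drugs already in use are left out of the medication tables

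*SAP*

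**What the plan says.** SAP 3.3.2.4 opens by describing the analysis as covering "TEAEs occurring/concomitant medication taken during the safety randomised period", with a parallel phrase for the on-selumetinib period. Its operative sentence for the randomised period then says that "an adverse event (AE) or a concomitant medication is considered treatment emergent during the safety randomised period if the start date/time of the event" lies between first dose and the end of that period. Worsening is offered as an alternative route, but for AEs only. The sentence for the second period has the same form: "An AE or a concomitant medication is considered treatment-emergent during the on-selumetinib period if the start date/time of the event" falls after the first selumetinib dose. That dose is Cycle 1 Day 1 for the selumetinib arm and the crossover date for the placebo arm.

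SAP 4.1.8.1 takes a different line. "Concomitant medications are those with a stop date on or after the first dose date of study intervention", and these "and could have started prior to or during treatment". Prior medications are those that had stopped before first dose.

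SAP 4.1.8.2 plans three summaries: prior, allowed concomitant and disallowed concomitant. On the last two it says: "The summary tables of allowed and disallowed concomitant medications will be presented for medications during the on-treatment safety randomised period using the FAS". The on-selumetinib versions use the Extended Selumetinib FAS. For the period definitions it cites 3.3.2.3, which gives calendar boundaries and no rule for placing a medication in a period.

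**The concern.** A start-date rule suits adverse events, where the interest is in what began or worsened on treatment. It does not suit concomitant medication, where the interest is in what the participant was exposed to. Under 3.3.2.4 as written, a drug can be concomitant by definition and yet belong to no period.

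Two groups of drugs are at stake. The first is disallowed treatment. Protocol exclusion criteria 14 and 17 to 19 and Table J18 require certain treatments to be stopped before first dose. A participant who failed to stop one has, by construction, a start date before Day 1, so the rule removes that use from the table of disallowed medications. The second is long-standing treatment in general. Inclusion criterion 3 requires any chronic PN pain medication to be stable at entry, and Protocol 6.5 foresees that some of it may be a CYP inhibitor present when selumetinib is started.

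The same allowed and disallowed tables are planned for the China submission (SAP Table 19).

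**Working it through.** The plan states no figure to reproduce, so the check is to classify medication patterns under each rule.

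**Inputs.** Cycles are 28 days, so the last day of Cycle 12 is Day 12 × 28 = 336 and crossover is Day 337. Illustrative assumptions: last selumetinib dose on Day 700, so the on-selumetinib period ends on Day 700 + 30 = 730. The randomised period (R) is taken as Days 1–337 for placebo and Days 1–336 for selumetinib. The on-selumetinib period (O) is Days 337–730 for placebo and Days 1–730 for selumetinib.

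**Rules.**
- SAP 4.1.8.1: prior if stop < Day 1; concomitant if stop ≥ Day 1.
- SAP 3.3.2.4: in a period if period start ≤ drug start ≤ period end.
- Overlap (drug in use during the period): drug start ≤ period end, and drug stop ≥ period start or ongoing.

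| Pattern (start to stop) | 4.1.8.1 | 3.3.2.4: placebo | 3.3.2.4: selumetinib | Overlap: placebo | Overlap: selumetinib |
|---|---|---|---|---|---|
| A: Day −60 to −5 | prior | none | none | none | none |
| B: Day −60 to 100 | concomitant | none | none | R | R, O |
| C: Day −60, ongoing | concomitant | none | none | R, O | R, O |
| D: Day 100 to 200 | concomitant | R | R, O | R | R, O |
| E: Day 100, ongoing | concomitant | R | R, O | R, O | R, O |
| F: Day 400 to 450 | concomitant | O | O | O | O |

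**Reading the table.**
1. Patterns B and C are concomitant and not prior, yet under 3.3.2.4 they enter no period table in either arm. As 4.1.8.2 plans only prior, allowed and disallowed summaries, they appear in none of them.
2. Pattern E in a placebo participant is missing from the on-selumetinib table although the drug is taken on selumetinib. Here the conflict is not with 4.1.8.1, which is anchored to the first dose of study intervention. It is with the stated aim of 3.3.2.4 and with the by-period tabulation in 4.1.8.2.
3. Patterns A, D and F come out the same under both rules.
4. Under overlap, no concomitant pattern is left without a table.

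**Effect of date imputation (SAP 3.3.5.1).** If the drug is ongoing or ended on or after first dose, a start date with a missing day in the month of first dose, or with missing day and month in the year of first dose, is set to the first dose date. A completely missing start date is generally set there too. Such drugs satisfy the start-date rule for the randomised period. A drug with a fully recorded earlier start does not, so under 3.3.2.4 inclusion would depend partly on how completely the date was recorded.

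**The case against.** The strongest reply is that the table section never invokes the start-date rule. SAP 4.1.8.2 cites 3.3.2.3, concomitant is defined by stop date in the adjoining subsection, and no planned medication table is labelled treatment-emergent. SAP 3.3.5.1 also separates the two ideas, imputing dates to decide whether an AE is treatment-emergent and whether a medication is concomitant. A programmer working from 4.1.8 could reasonably include ongoing drugs. This stands in part: the omission follows only if 3.3.2.4 is applied as written. It does not remove the conflict. The start-date rule is the only one that assigns medications to periods, and it sits under subheadings that name concomitant medication. Two programmers could build different tables from this text.

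Three stronger readings are tempting, and the documents do not support them.
- A reader might infer that every drug ongoing at first dose is certain to be lost. The cross-reference to 3.3.2.3 and the imputation rules both prevent that conclusion.
- A reader might infer that baseline chronic PN pain medication would vanish from the report. SAP 4.2.11.6 summarises its analgesic-ladder category and score at baseline and each cycle from the eDiary, with a shift table, and 4.1.8.2 lists all concomitant medications. A disallowed drug that was not stopped would also be a protocol deviation. Important deviations are tabulated under 4.1.3.2, though whether this one counts as important depends on a deviation plan that is not among the documents.
- A reader might blame this rule for the on-selumetinib columns not being comparable. Those columns cover different periods by arm under any rule, and 3.3.2.4 already calls the on-selumetinib TEAE presentation non-comparative.

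**Conclusion.** The inconsistency is real, and the effect is small. SAP 3.3.2.4 contradicts its own stated aim, the stop-date definition in 4.1.8.1 and the by-period tabulation in 4.1.8.2. Applied literally, it leaves drugs with a known start before first dose out of every medication summary, and leaves drugs started on placebo and continued out of the on-selumetinib table.

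Only descriptive tables of allowed and disallowed medication are affected. Listings remain complete, chronic PN pain medication has its own summaries, and no efficacy or AE result changes. The documents do not say how many participants would be affected. The cap of about 106 of 146 participants with a pain score of at least 3 (106/146 = 73%) makes ongoing medication at Day 1 plausible, but it does not measure it. The conclusion about omitted drugs assumes that 3.3.2.4 governs the tables; if 4.1.8 governs, what remains is an unresolved contradiction in the SAP.

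**What to change.** - In SAP 3.3.2.4, restrict the start/worsening (treatment-emergent) rule to AEs.
- Assign a medication to a period if its use overlaps that period: start on or before period end, and stop on or after period start or ongoing.
- State that the period boundaries are those of 3.3.2.3. This needs saying because the two sections differ: for the selumetinib arm, 3.3.2.3 ends the randomised period at kit dispensing at or after the Cycle 12 Day 28 visit, with an earlier end the day before subsequent therapy, while 3.3.2.4 uses the last dose of Cycle 12.
- Make 4.1.8.2 refer to this rule as well as to 3.3.2.3.

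The cost is one sentence, one derivation and one cross-reference, best settled before the tables are finalised. A drug may then be counted in both periods, which a table footnote should say. The on-selumetinib columns remain non-comparative because the periods differ by arm.
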